11.1.3 Methods for Evaluation of Measurable Disease

All measurements should be taken and recorded in metric notation using a ruler or calipers. The same method of assessment and the same technique should be used to characterize each identified and reported lesion at baseline and during follow-up.

Clinical Lesions: Clinical lesions will only be considered measurable when they are superficial (e.g., skin nodules and palpable lymph nodes) and ≥ 10 mm diameter as assessed using calipers (e.g. skin nodules). For the case of skin lesions, documentation by colour photography including a ruler to estimate the size of the lesion is recommended. When lesions can be evaluated by both clinical exam and imaging, imaging evaluation should be undertaken since it is more objective and may also be reviewed at the end of the study.

Chest X-ray: Lesions on chest X-ray are acceptable as measurable lesions when they are clearly defined and surrounded by aerated lung. However, CT is preferable.

CT & MRI: CT is the best currently available and reproducible method to measure lesions selected for response assessment. CT should be performed with slice thickness of 5 mm or less. When CT scans have slice thickness greater than 5 mm, the minimum size for a measurable lesion should be twice the slice thickness. MRI is also acceptable in certain situations (e.g. for body scans).

Ultrasound: Ultrasound is not useful in assessment of lesion size and should not be used as a method of measurement. Ultrasound examinations cannot be reproduced in their entirety for independent review at a later date and, because they are operator dependent, it cannot be guaranteed that the same technique and measurements will be taken from one assessment to the next. If new lesions are identified by ultrasound in the course of the study, confirmation by CT or MRI is advised.

Cytology, Histology: These techniques can be used to differentiate between PR and CR in rare cases. The cytological confirmation of the neoplastic origin of any effusion that appears or worsens during treatment can be considered if the measurable tumour has met criteria for response or stable disease in order to differentiate between response (or stable disease) and progressive disease.

11.1.4 RECIST/ iRECIST Assessment of Disease

Response

All patients will have their BEST RESPONSE from the start of study treatment until the end of treatment classified as outlined below:

Complete Response (CR): disappearance of *target* and *non-target* lesions and normalization of tumour markers. Pathological lymph nodes must have short axis reduction to < 10mm (Note: continue to record the measurement even if < 10mm and considered CR). Residual lesions (other than nodes < 10mm) thought to be non-malignant should be further investigated (by cytology specialized imaging or other techniques as appropriate for individual cases [ref RECIST 1.1]) before CR can be accepted. Confirmation of response is required

Partial Response (PR): at least a 30% decrease in the sum of measures (longest diameter for tumour lesions and short axis measure for nodes) of target lesions, taking as reference the baseline sum of diameters. Non target lesions must be non-PD. Patients with CR/iCR or PR/iPR should have scans repeated after 4 weeks, but no more than 8 weeks, to confirm response.

Stable Disease (SD): Neither sufficient shrinkage to qualify for PR nor sufficient increase to qualify for PD taking as reference the smallest sum of diameters on study

Progressive Disease (PD): at least a 20% increase in the sum of diameters of measured lesions taking as references the smallest sum of diameters recorded on study (including baseline) AND an absolute increase of $\geq 5\text{mm}$. Appearance of new lesions will also constitute progressive disease (including lesions in previously unassessed areas). When the patient has only non-measurable disease, unequivocal progression of non-target disease may be accepted as evidence of disease progression, where the overall tumour burden has increased sufficiently to merit discontinuation of treatment or where the tumour burden appears to have increased by at least 73% in volume. Modest increases in the size of one or more non-target lesions are NOT considered unequivocal progression. If the evidence of PD is equivocal (target or non-target), treatment may continue until the next assessment, but if confirmed, the earlier date must be used.

Patients that are clinically well may continue on therapy following RECIST progression with new lesions or increase in target lesions if the increase in disease burden does not meet the definition of PD by immune response criteria [Seymour 2017]. In this situation, patients do not have unequivocal progression until immune response criteria are met (see Table 10 below).

Table 10: Integration of Target, non-Target and New Lesions into Response Assessment

Target Lesions	Non-Target Lesions	New Lesions*	Overall Response	Best Response for this Category also Requires
Target lesions ± non target lesions				
CR	CR	No	CR	Normalization of tumour markers, tumour nodes <10mm
CR	Non-CR/Non-PD	No	PR	
CR	Not all evaluated	No	PR	
PR	Non-PD/ not all evaluated	No	PR	
SD	Non-PD/ not all evaluated	No	SD	documented at least once \geq 4 wks. from baseline
Not all evaluated	Non-PD	No	NE	
PD	Any	Any	PD	
Any	PD	Any	PD	
Any	Any	Yes*	PD	
Non target lesions ONLY				
No Target	CR	No	CR	Normalization of tumour markers, tumour nodes < 10mm
No Target	Non-CR/non-PD	No	Non-CR / non-PD	
No Target	Not all evaluated	No	NE	
No Target	Unequivocal PD	Any	PD	
No Target	Any	Yes*	PD	
Note: Patients with a global deterioration of health status requiring discontinuation of treatment without objective evidence of disease progression at that time should be reported as “symptomatic deterioration”. This is a reason for stopping therapy, but is NOT objective PD. Every effort should be made to document the objective progression even after discontinuation of treatment.				
[*] Investigators should record all new lesions; if the new lesion is felt to be equivocal, treatment may be continued pending further assessments – see New Lesion section below.				

Immune-Related Response Assessment (iRECIST)

Overall response will also be assessed using iRECIST [Seymour 2017]. Immunotherapeutics may result in infiltration of immune cells leading to transient increase in the size in malignant lesions, or undetectable lesions becoming detectable. The criteria are identical to those of RECIST 1.1 in many respects but have been adapted to account for instances where an increase in tumour burden, or the appearance of new lesions, does not reflect true tumour progression.

Key differences are described below. All responses defined using iRECIST criteria are designated with a prefix. iRECIST time-points and best overall responses will be recorded separately.

Confirming Progression

Unlike RECIST 1.1, iRECIST requires the confirmation of progression and uses the terms iUPD (unconfirmed progression) and iCPD (confirmed progression). Confirmatory scans should be performed at least 4 weeks, but no longer than 8 weeks after iUPD.

iCPD is confirmed if further increase in tumour burden, compared to the last assessment, is seen as evidenced by one or more of the following:

- Continued increase in tumour burden (from iUPD) where RECIST 1.1 definitions of progression had been met (from nadir) in target, non-target disease or new lesions
 - Progression in target disease worsens with an increase of at least 5 mm in the absolute value of the sum
 - Continued unequivocal progression in non-target disease with an increase in tumour burden
 - Increase in size of previously identified new lesion (s) (an increase of at least 5 mm in the absolute value of the sum of those considered to be target new lesions) or additional new lesions.
- RECIST 1.1 criteria are met in lesions types (target or non-target or new lesions) where progression was not previously identified, including the appearance of additional new lesions.

If iUPD is not confirmed at the next assessment, then the appropriate response will be assigned (iUPD if the criteria are still met, but no worsening, or iSD, iPR or iCR if those criteria are met compared to baseline). As can be seen in **Table 11**, the prior documentation of iUPD does not preclude assigning iCR, iPR, or iSD in subsequent time-point assessments or as best overall response (BOR) providing that iCPD is not documented at the next assessment after iUPD. Patients who have iUPD and are not clinically stable should be designated as not clinically stable in the case report form.

New Lesions

New lesions should be assessed and measured as they appear using RECIST 1.1 criteria (maximum of 5 lesions, no more than 2 per organ, at least 10 mm in long axis (or 15 mm in short axis for nodal lesions), and recorded as New Lesions-Target (NLT) and New Lesion-Non-Target (NLNT) to allow clear differentiation from baseline target and non-target lesions.

New lesions may either meet the criteria of NLT or NLNT to drive iUPD (or iCPD). However, the

measurements of NLT should not be included in the sum of measures of original target lesions identified at baseline. Rather, these measurements will be collected on a separate table in the case record form.

PD is confirmed in the New Lesion category if the next imaging assessment, conducted at least 4 weeks (but not more than 8 weeks) after iUPD, confirms further progression from iUPD with either an increase of at least 5 mm in the absolute value of the sum of NLT OR an increase (but not necessarily unequivocal increase) in the size of NLNT lesions OR the appearance of additional new lesions.

Table 11: Time-point (TP) iResponse

Target Lesions*	Non-Target Lesions*	New Lesions*	Time Point Response	
			No prior iUPD**	Prior iUPD**; ***
iCR	iCR	No	iCR	iCR
iCR	Non-iCR/Non-iUPD	No	iPR	iPR
iPR	Non-iCR/Non-iUPD	No	iPR	iPR
iSD	Non-iCR/Non-iUPD	No	iSD	iSD
iUPD with no change OR decrease from last TP	iUPD with no change OR decrease from last TP	Yes	NA	NLs confirm iCPD if NLs were previously identified and have increased in size (≥ 5 mm in SOM for NLT or any increase for NLNT) or number. If no change in NLs (size or number) from last TP, remains iUPD
iSD, iPR, iCR	iUPD	No	iUPD	Remains iUPD unless iCPD confirmed based in further increase in size of NT disease (need not meet RECIST 1.1 criteria for unequivocal PD)
iUPD	Non-iCR/Non-iUPD or iCR	No	iUPD	Remains iUPD unless iCPD confirmed based on: 
 - further increase in SOM by at least 5 mm, otherwise remains iUPD
iUPD	iUPD	No	iUPD	Remains iUPD unless iCPD confirmed based on further increase in: 
 - previously identified target lesion iUPD SOM ≥ 5 mm and / or - NT lesion iUPD (prior assessment need not be unequivocal PD)
iUPD	iUPD	Yes	iUPD	Remains iUPD unless iCPD confirmed based on further increase in: 
 - previously identified T lesion iUPD ≥ 5 mm and / or - previously identified NT lesion iUPD (need not be unequivocal and / or - size or number of new lesions previously identified
Non-iUPD/PD	Non-iUPD/PD	Yes	iUPD	Remains iUPD unless iCPD confirmed based on 
 - increase in size or number of new lesions previously identified

* Using RECIST 1.1 principles. If no pseudoprogression (PSPD) occurs, RECIST 1.1 and iRECIST categories for CR, PR and SD would be the same.

** In any lesion category.

*** Previously identified in assessment immediately prior to this time point.

Vascular Thrombosis Response Evaluation

There are no validated guidelines to monitor and report vascular thrombosis response. Consistent with RECIST1.1, thrombosis will be considered non-measurable disease. Vascular thrombosis response should be recorded using the following guidelines:

iCR thrombosis:

Complete resolution of thrombosis, with recanalization of vessel.

iPR thrombosis: any of

- a) Partial recanalization of thrombosis (if prior complete blockage)
- b) Unequivocal reduction in the maximal girth of thrombosis
- c) Unequivocal reduction in the volume, or elimination, of arterial enhancing portion of thrombosis

iPD thrombosis: any unequivocal, unambiguous increase in the volume of new or existing enhancing thrombosis

Note that for “unequivocal progression” of thrombosis (non-measurable disease), the increase in overall tumor burden (enhancing thrombosis) must be comparable to the increase required for iRECIST definition of PD of measurable disease.

iSD thrombosis: any of

- a) No change or small changes that do not meet the above criteria for iPR or iPD, taking as reference the smallest sum diameters while on study.
- b) Increase in the volume of non-enhancing thrombosis
- c) New bland non-enhancing thrombosis

11.1.5 Progression-Free Survival

Progression free survival (PFS) is defined as the duration of time from start of treatment to time of progression or death, whichever occurs first.

11.1.6 Response Review

All iCR and iPR responses will be reviewed by an expert(s) independent of the study at the subject's completion of the study by simultaneous review of subject files and radiologic images.

12. DATA REPORTING / REGULATORY REQUIREMENTS

Adverse event lists, guidelines, and instructions for AE reporting can be found in Section 7 above (Adverse Events: List and Reporting Requirements).

12.1 Data Collection and Reporting

All data obtained in the clinical trial described in this protocol will be reported on eCRFs in the Medidata Electronic Document Capture system (Medidata). Data reported on eCRFs should be consistent with the source documents and verifiable. All data for the primary and secondary endpoints will be source verified prior to publication. The Investigator will review the data and electronically sign the eCRFs to acknowledge agreement with the data entered. Data will be entered into Medidata and will be used for developing tables and listings for the final study report.

Prior to the start of the study, the Investigator will complete a Site Participants Log showing the signatures and handwritten initials of all individuals who are authorized to make or change entries on source documents and eCRFs.

12.2 Source Documents

Source documents refer to the original documents, data, and records where the first recording of a data point occurred. Examples of source documentation include, but are not limited to:

Hospital records, clinical and office charts, laboratory notes, memoranda, subjects' diaries or evaluation checklists, pharmacy dispensing records, recorded data from automated instruments, copies or transcriptions certified after verification as being accurate copies, microfiches, photographic negatives, microfilm or magnetic media, x-rays, subject files, and records kept at the pharmacy, at the laboratories and at medico-technical departments involved in the clinical trial)

Please ensure that source document entries are attributable, legible, contemporaneous, original, and accurate. Note that sign-off of source documents should be attributable to a single record and "bracketing" multiple entries on source document pages for a single signature is not allowed. Corrections to source document entries should only be completed by drawing a single line through the previous entry and then recording the corrected data, initialing the change, and dating the change. Only the individual that initially recorded the data should make any corrections.

12.3 Retention of Subject Records and Study Files

The ICH guidance document, Good Clinical Practice: Consolidated Guidelines (ICH Guidance Document E6) (1997) states that the investigator and sponsor shall retain study records relating to the study until at least 2 years after the last approval of a marketing application and until there are no pending or contemplated marketing applications, or at least 2 years have elapsed since the formal discontinuation of clinical development of the investigational product. In the event of a trial discontinuation, sponsor records should also be kept for a minimum of 2 years. Per Health Canada, all original records should be maintained for 25 years after the above requirements are satisfied and the final report has been issued. Records contained in the Clinical Trial Application should be maintained on file for at least 25 years. We will comply with these regulations. The Sponsor will notify sites when documents are to be destroyed.

12.4 Site and Study Closure

Upon completion of the study, the following activities, when applicable, will be completed by the Central Office in conjunction with the Investigator, as appropriate:

- Collection of study materials (i.e., specimen collection kits, drug shippers, etc.)
- Data clarifications and/or resolutions
- Accounting, reconciliation, and final disposition of used and unused study medication
- Review of site study records for completeness

If the Sponsor or Investigator or appropriate regulatory officials identify conditions arising during the study that indicate that the study should be halted or that the study center should be terminated, this action may be taken after appropriate consultation among the Sponsor and Investigator. Conditions that may warrant termination of the study include, but are not limited to, the following:

- The discovery of an unexpected, serious, or unacceptable risk to the subjects enrolled in the study
- A decision on the part of the Sponsor to suspend or discontinue testing, evaluation, or development of the product
- Failure of the Investigator to enroll subjects into the study at an acceptable rate
- Failure of the Investigator to comply with pertinent regulations of appropriate regulatory authorities
- Submission of knowingly false information to the Sponsor, or appropriate regulatory authority
- Insufficient adherence to protocol requirements
- Refusal of the Investigator to supply source documentation of work performed in this clinical trial

Study termination and follow-up will be performed in compliance with the conditions set forth in the International Conference on Harmonisation (ICH) sixth efficacy publication (E6) on Good Clinical Practice, ICH E6 4.12, ICH E6 4.13, ICH E6 5.20, and ICH E6 5.21.

13. STATISTICAL CONSIDERATIONS

13.1 Study Design/Endpoints

This is a single-arm, non-comparative, open-label phase II study of combination treatment with pembrolizumab and SBRT in patients with advanced HCC who have experienced disease progression after treatment with sorafenib/lenvatinib.

Study objectives are stated in Section 1.1 to 1.3.

The primary endpoint of the study is overall response rate, defined as the proportion of the subjects in the study population who have a complete response (iCR) or partial response (iPR), as defined by iRECIST, at any time on study treatment. Of note this may follow a period of iUPD.

13.2 Sample Size/Accrual Rate

Given the preliminary results with nivolumab, we would expect that pembrolizumab alone would produce responses in 15% of patients.²⁴ We hypothesize that combining pembrolizumab with SBRT will increase the ORR to 40%, a clinically meaningful increase in systemic response rate and indicative of significant activity (Note: ORR is a composite sum of irradiated local tumor and other measurable metastatic disease - local radiotherapy response, systemic pembrolizumab response and potential abscopal effect on all measurable disease).

With 90% power, we would need to accrue 22 evaluable patients in a two-stage study design, with a one-sided significance level of 10%. If 2 or more patients show response from the first 10 evaluable patients, we will continue to accrue to a total of 22 evaluable patients. We expect to accrue up to 27 patients as some patients may not be evaluable for the primary endpoint. A total number of 6 or more responders in 22 evaluable patients would be considered to reject the null hypothesis. We expect to accrue 2-3 patients per month, leading to complete accrual in 12 months following study activation.

13.3 Analysis of Primary Endpoint

Overall Response Rate (ORR)

ORR is defined as the proportion of the subjects in the study population who have a complete response (iCR) or partial response (iPR), as defined by iRECIST, at any time on study treatment. This is noting that radiated lesions will count as target lesions provided there has been demonstrated progression in the lesion.

The point estimate and 95% confidence interval for ORR will be provided using the Clopper and Pearson exact binomial method. An interim analysis for futility will be undertaken when response data are available on the first 10 evaluable subjects enrolled. If ≤ 1 responses are documented, the trial will be stopped. If 2 or more responses (iCR or iPR) are documented, the study will continue to full accrual. Subjects who are inevaluable for the primary endpoint will be replaced.

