The primary objective of the study is to assess the ORR of the combination of SBRT and pembrolizumab, as measured by RECIST 1.1. /iRECIST. Given the preliminary results with nivolumab, we would predict pembrolizumab alone to produce an ORR of approximately 15%. We hypothesize that combining pembrolizumab with SBRT will increase the ORR to 40%, a clinically meaningful increase in systemic response rate and indicative of significant activity. With 90% power, we would need to accrue 22 subjects in a two-stage study design, with a one-sided significance level of 10%. If 2 or more subjects show response from the first 10, we will continue to accrue to a total of 27, as we expect that some subjects will not be evaluable for the primary endpoint. A total number of 6 or more responders in 22 evaluable subjects would be considered to reject the null hypothesis. Response will be defined as best response at any time on study treatment.

Secondary analyses will be performed without pre-specified assumptions of efficacy, given the lack of data in this setting.

LIST OF ABBREVIATIONS

AE	Adverse Event
AFP	Alpha Fetoprotein
BCLC	Barcelona Clinic for Liver Cancer (staging)
BP	Blood Pressure
CBC	Complete Blood Count
CI	Confidence Interval
CP	Child-Pugh (Score)
CR	Complete Response
CT	Computed Tomogram
CTCAE	Common Terminology Criteria for Adverse Events
eCRF	Electronic Case Report Form
DDP	Drug Development Program
DRESS	Drug Rash with Eosinophilia and Systemic Symptom
cfDNA	Cell-free DNA
ctDNA	Circulating Tumor DNA
ECOG	Eastern Co-operative Oncology Group
GCP	Good Clinical Practice
GTV	Gross Tumour Volume
Gy	Gray
HCC	Hepatocellular Carcinoma
HBV	Hepatitis B Virus
HCV	Hepatitis C Virus
ICH	International Conference on Harmonization
irAE	Immune Related Adverse Event
iRECIST	immune related modified RECIST 1.1
IRB	Institutional Review Board
LFT	Liver Function Tests
MRI	Magnetic Resonance Imaging
NA	Not Applicable
NAFLD	Non-Alcoholic Fatty Liver Disease
NASH	Non-Alcoholic Steatohepatitis
NE	Not Evaluable
NK	Natural Killer
NTCP	Normal Tissue Complication Probability
OAR	Organs at Risk
ORR	Overall Response Rate
OS	Overall Survival
OTN	Ontario Telemedicine Network
PBMC	Peripheral Blood Mononuclear Cell
PD	Progressive Disease
PD-1	Programmed Death-1
PDL-1	Programmed Death Ligand-1
PFS	Progression Free Survival
PTV	Planning target volume

PM	Princess Margaret Cancer Centre
PR	Partial Response
RECIST	Response Evaluation Criteria in Solid Tumor
REB	Research Ethics Board

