AFP	X	X			X	X	X	X	X	X	
Biopsy for correlative studies	X										
Optional biopsy for correlative studies					X ^k						
Blood for ctDNA/methylation ^l		X		X				X		X	
Blood for cytokine analysis ^l		X		X	X	X		X		X	
Survival status											X

All assessments may be performed up to 2 working days prior to scheduled day.

A: Pembrolizumab 200 mg IV Q3W
 B: SBRT as per Section 5.1.2, commencing Cycle 1 Day 2, consisting of 5 fractions over 5-15 days
 a: Albumin, alkaline phosphatase, total bilirubin, bicarbonate, calcium, chloride, creatinine, glucose, LDH, phosphorus, potassium, total protein, AST, ALT, sodium.
 b: Serum pregnancy test (women of childbearing potential).
 c: See Section 5.4 for post-treatment follow-up requirements.
 d: Blood pressure, temperature, pulse, O₂ saturation, and respiratory rate.
 e: Day of assessment while on SBRT may vary due to weekends, but should be as close to day 3 as possible.
 f: See Appendix 4 for vascular thrombosis staging chart.
 g: All patients should have baseline Hepatitis B screening which should include: HbsAg, Anti-Hbs and Anti-Hbc (total+IgM). For patients with known hepatitis B, or if they have been deemed infected through baseline screening, additional test should include: HBV viral load (DNA), HbeAg and Anti-Hbe. If HBV viral load has been performed within previous 3 months a repeat test is not required. If Hepatitis B Testing has been performed for eligibility less than 28 days prior to start of therapy it is not required to be repeated again as a part of Baseline (Pre-study) evaluations.
 h: All patients should have baseline Hepatitis C screening which should include: Anti-HCV. For patients with known hepatitis C, or if they have been deemed infected through baseline screening, HCV viral load (RNA) should be performed. If HCV viral load has been performed within previous 3 months a repeat test is not required. If Hepatitis C Testing has been performed for eligibility less than 28 days prior to start of therapy it is not required to be repeated again as a part of Baseline (Pre-study) evaluations.
 i: Patients who come off study treatment for reasons other than radiological progression are to have tumor measurements and disease response evaluated every 3mo ± 14 days until documented progression per iRECIST or start of new therapy.

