 j: Only required if the patient has a known history of Hepatitis B and the testing has not been completed previously. If testing has been done previously, a repeat test is not required. If Anti-HDV Testing is required, this must be done ≤ 28 days prior to the start of therapy.
 k: Optional biopsy to be done between 3-6 weeks on study for patients that have consented to procedure
 l: Research bloods to be drawn prior to Pembrolizumab administration. Research blood must be collected on-site at Princess Margaret Cancer Centre.
 m: Radiologic evaluation and tumor measurements should be performed at 12 weeks on treatment and then repeated every 10 weeks thereafter (± 2 weeks). CT scans should be performed at planned time points regardless of any dose delays.

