11. MEASUREMENT OF EFFECT

11.1 Antitumor Effect – Solid Tumors

For the purposes of this study, subjects should be re-evaluated for response every 12 weeks. In addition to a baseline scan, confirmatory scans should also be obtained 4-8 weeks following initial documentation of objective response.

Note, response in the irradiated volume is challenging to assess before 3 months post radiation therapy due to radiation change in the surrounding liver. Even at 3 months, changes in the surrounding liver around the HCC may represent radiation treatment change, rather than tumor progression. Thus, review of images by experienced radiologists is required, as is importance of relaying radiation information to the radiologists, to avoid inaccurate labeling of progression when liver changes are due to radiation effect on the liver.

Response and progression will be evaluated in this study using both RECIST 1.1 and the new criteria proposed by immune modified Response Evaluation Criteria in Solid Tumors (iRECIST) guideline (Seymor 2017). Changes in the largest diameter (uni-dimensional measurement) of the tumor lesions and the shortest diameter in the case of malignant lymph nodes are used in the iRECIST criteria. Overall response will be assessed, as well as response in lesions outside the SBRT treatment field. These criteria keep the uni-dimensional measurement of RECIST, but incorporate the concept of unconfirmed progression (iUPD) noted with the use of immunotherapy. In the case of new lesions, assessments continue as per RECIST 1.1 but are recorded in a separate case report form. Contrasting to RECIST 1.1 new lesions may result in iUPD but immune confirmed progression (iCPD) is only assigned on the basis of this category if at next assessment additional new lesions appear or an increase in size of new lesions is seen (≥ 5 mm for sum of new lesion target or any increase in new lesion non-target); the appearance of new lesions when none have previously been recorded, can also confirm iCPD. iUPD may occur before iPR, iCR or iSD, in contrast to RECIST 1.1 where progression could not occur. Notable in this study, radiated lesions will be counted as part of the response criteria, an exception to the rules of RECIST 1.1.

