13.4 Analysis of Secondary Endpoints

Response in non-irradiated lesions

Response in non-irradiated lesions is defined as the proportion of subjects in the study population who demonstrate iCR or iPR, by iRECIST 1.1, when tumors within the radiotherapy treatment field are excluded from analysis. Subjects will be ineligible for this analysis if no RECIST-measurable lesions exist outside the radiotherapy treatment field.

The point estimate and 95% confidence interval for ORR will be provided using the Clopper and Pearson exact binomial method.

Duration of Response (DOR)

For subjects who demonstrate iCR or iPR, by iRECIST, DOR is defined as the time from first documented evidence of iCR or iPR until disease progression or death due to any cause, whichever occurs first.

DOR will be estimated by the Kaplan-Meier method, and the Cox proportional hazard regression model will be used to analyze the effects of factors, in addition to treatment, that may be associated with DOR.

Progression-Free Survival (PFS)

PFS is defined as the time from enrollment until the date of objective disease progression, by iRECIST, or death (by any cause in the absence of progression).

PFS will be estimated by the Kaplan-Meier method, and the Cox proportional hazard regression model will be used to analyze the effects of factors, in addition to treatment, that may be associated with PFS.

Overall Survival (OS)

OS is defined as the time from study enrollment to death due to any cause.

OS will be estimated by the Kaplan-Meier method, and the Cox proportional hazard regression model will be used to analyze the effects of factors, in addition to treatment, that may be associated with OS.

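### The primary ORR counts responses only while on study treatment, so a response first seen on a required scan after a non-progression stop is not counted

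*Combined protocol and SAP*

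**What the plan says.** Four places set the response window, and they agree.

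- Section 13.3 counts iCR or "partial response (iPR), as defined by iRECIST, at any time on study treatment".
- Section 13.1 has the same limit and adds only that a response may come after unconfirmed progression: "at any time on study treatment. Of note this may follow a period of iUPD".
- The synopsis (Statistics): "Response will be defined as best response at any time on study treatment".
- Section 11.1.4: "All patients will have their BEST RESPONSE from the start of study treatment until the end of treatment classified as outlined below".

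Imaging does not stop with treatment. Study Calendar note i: "Patients who come off study treatment for reasons other than radiological progression are to have tumor measurements and disease response evaluated every 3mo", until progression or new therapy. Section 5.4 likewise follows disease status every 90 days in these subjects.

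On timing, note m says "Radiologic evaluation and tumor measurements should be performed at 12 weeks on treatment", then every 10 weeks, each +/- 2 weeks. Section 11.1 warns that "response in the irradiated volume is challenging to assess before 3 months post radiation" therapy. SBRT is given once, in 5 fractions over 5 to 15 days from day 2 of cycle 1 (Section 5.1).

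Two rules settle who is in the denominator, and they do not fit together. Section 13.6.2 keeps every eligible subject who received study medication in the primary analysis and scores missing data as non-response. Section 11.1.1 calls a subject evaluable only after at least one cycle and a disease re-evaluation, and Section 13.3 replaces inevaluable subjects.

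**The concern.** Section 2.3 says the composite ORR is meant to evaluate SBRT and pembrolizumab as a package. The radiation part is complete within about two weeks, but its effect may not be readable for about three months. The response window, however, is tied to how long the subject stays on pembrolizumab.

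Take a subject who completes SBRT, permanently stops pembrolizumab for an adverse event before week 12 without progression, and has a confirmed 30% or greater decrease on the required follow-up scans. The protocol collects those scans, but the primary endpoint ignores them. A subject who is stable at week 12, stops for toxicity and responds later is treated the same way.

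At stake are the accuracy of the ORR and the decisions resting on small counts: 2 of 10 to continue and 6 of 22 to reject. One uncounted responder can change either decision.

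**Working it through.** **1. Scan timing.** SBRT starts on day 2 and lasts 5 to 15 days, so it ends between day 6 and day 16. Week 12 is day 85 (12 x 7 + 1). The first scan therefore falls 85 - 16 = 69 to 85 - 6 = 79 days after the last fraction. With the +/- 14-day window the range is 55 to 93 days. Most of that range lies before the three-month point named in Section 11.1.

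**2. The plan's own design.** Inputs from Section 13.2: null rate 15%, target 40%; stop at 1 or fewer responses in 10; reject at 6 or more in 22. With X1 ~ Bin(10, p) and X2 ~ Bin(12, p):

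P(reject) = sum over x from 2 to 10 of P(X1 = x) x P(X2 >= 6 - x)

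P(stop at stage 1) = (1 - p)^10 + 10p(1 - p)^9

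- p = 0.15: P(reject) = 0.091, within the 10% limit.
- p = 0.40: P(reject) = 0.903, matching the stated 90%.
- p = 0.40: P(stop) = 0.6^10 + 10 x 0.4 x 0.6^9 = 0.0060 + 0.0403 = 0.046.

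The stated figures reproduce.

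**3. Effect of the window.** Let d be the share of true responders whose response is first seen off treatment. The documents give no value, so d is an assumption shown over a range. This step also assumes that 40% is the any-time response rate and that Section 13.6.2 governs the denominator. The counted rate is then 0.40 x (1 - d). The last column applies the same share under the null, 0.15 x (1 - d).

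| d | Counted rate | Power | P(stop at stage 1) | Type I error |
|---|---|---|---|---|
| 0 | 0.40 | 0.903 | 0.046 | 0.091 |
| 5% | 0.38 | 0.870 | 0.060 | 0.074 |
| 10% | 0.36 | 0.828 | 0.076 | 0.060 |
| 20% | 0.32 | 0.718 | 0.121 | 0.037 |

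If early stoppers respond less often, the loss shrinks. Suppose 5% of subjects stop early and respond at half the target rate. The counted rate is then 0.40 - 0.05 x 0.20 = 0.39 and power is 0.887.

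**4. The other denominator.** Suppose only an on-treatment scan counts as re-evaluation. A subject with no such scan is then inevaluable under Section 11.1.1 and replaced under Section 13.3. The response is still discarded, but the 22 are not diluted and the table does not apply to that subject. This reading does not reach a subject already scanned as stable on treatment, who is evaluable either way.

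**The case against.** The strongest reply is that the window is a deliberate, consistently worded choice, and a conservative one: it cannot inflate type I error. That stands. Preferring a longer window is a preference about what to estimate, and the plan contains no arithmetic error here.

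The remaining objections each warn against a stronger inference.

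- **That the trial lacks its 90% power.** Section 13.2 attaches 40% to the ORR, which the protocol defines on treatment. At an on-treatment rate of 40%, power is 0.903. The loss appears only if 40% is taken as an any-time rate, and no section says so.
- **That these subjects always dilute the 22.** This holds only if Section 13.6.2 prevails over Sections 11.1.1 and 13.3. The documents do not say which does.
- **That duration of response uses a different responder set.** Section 13.4 says "For subjects who demonstrate iCR or iPR, by iRECIST, DOR is defined as the time from first documented evidence of iCR or iPR" and states no on-treatment limit, nor does its definition of response in non-irradiated lesions. Silence is not a wider window: both could inherit the best-response definition in Section 11.1.4.
- **That a response first seen on treatment is lost if its confirmatory scan comes later.** Section 11.1.4 asks for the repeat at 4 to 8 weeks and does not say it must fall on treatment.
- **That the loss is about 14%.** Section 2.2.3 reports 3 of 22 patients stopping for adverse events on ipilimumab with SBRT in melanoma. The drug and tumor differ and the timing is not given, so it should not anchor d.

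Dose holds are also not stops. Note m keeps scans at their planned times despite delays, so only permanent discontinuation matters.

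**Conclusion.** The point holds as a cheap improvement. Read literally, the plan discards valid responses to the treatment package when they are first documented after a non-progression stop, although the scans that would show them are already required. Where Section 13.6.2 governs, the ORR is biased down. Where the subject is replaced instead, the response is lost but the 22 are intact.

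The direction is conservative and the size is unknown. The fall in power to 0.870, 0.828 or 0.718 is conditional on the assumed d, on 40% being an any-time rate and on Section 13.6.2 governing. It is smaller if early stoppers respond less often. The text leaves two matters open that add to the case for clarification: the end of treatment is not defined for response purposes, and the evaluability and replacement rules conflict with the inclusion rule.

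**What to change.** - In the synopsis and Sections 11.1.4, 13.1 and 13.3, define best response as running from first dose until iCPD or the start of new anticancer therapy, whichever is first. State that this includes the follow-up scans under Study Calendar note i and Section 5.4.
- State that the 4-to-8-week confirmatory scan counts even if it falls after the last dose.
- State that the same window applies to response in non-irradiated lesions and to duration of response.
- Reconcile Sections 11.1.1 and 13.3 (evaluability, replacement) with Section 13.6.2 (all eligible treated subjects, missing as non-response).
- Keep the on-treatment ORR as a sensitivity analysis.

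The cost is wording only, since no new scans are needed. The downsides are small: a response after the last pembrolizumab dose is credited to the package, and some responses are read later, which may also delay the stage 1 count.
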